### Research Question and Aims

**Hypothesis:** Ablation of a portion of thyroid parenchyma with RFA technique will safely decrease thyroid hormone levels into the normal range with resolution of thyrotoxicosis.

**Aims, purpose, or objectives:**

We aim to study the changes in serum thyroid hormone levels in AIT patients after RFA therapy. This will address the hypothesis that ablation of a portion of thyroid parenchyma with RFA technique will safely decrease thyroid hormone levels into the normal range with resolution of thyrotoxicosis.

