**Rationale:**

RFA has been used for the management of thyroid nodules for more than a decade . We have employed it here at Mayo Clinic for the past 4 years with good results . While mainly used for non-toxic thyroid nodules there is encouraging data describing the response to RFA in the case of toxic thyroid adenomas. In total in the literature there are 47 cases of toxic nodules or toxic goiters that were treated with RFA (8-10) and in 50% of these cases the thyroid function normalized and in none of them did thyrotoxicosis worsened as a result of therapy. RFA has the capacity to lead to destruction of thyroid parenchyma and also to denaturation of stored thyroid hormone. Thus it seems to provide the perfect approach to target both mechanisms of AIT in an expeditious manner which is essential in these usually very sick individuals with coexistent cardiac co-morbidities. So far there is no reported data on the efficacy of RFA in AIT and this would be the first study on this therapy, hence our pilot study approach.

[figure not shown]

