## Study Design and Procedure

### STUDY DESIGN

This will be an open-label clinical trial that will target AIT patients that fail to respond to medical therapy. We will treat them with RFA therapy and then assess the clinical and biochemical response (primary objective) in the coming 4 weeks and continue to monitor the clinical response for a minimum of 3 months or until the resolution of the AIT episode, whichever occurs later. We expect that an individual will be thus in the trial for a total of 4-6 months. The safety of the RFA procedure will be assessed as well (secondary objective) in the first month after the procedure. We plan to enroll 5 patients to undergo the procedure and use a historical control group for comparison of clinical and biochemical outcomes. The study will take place at Mayo Clinic in Rochester, MN and will recruit both from our out-patient as well as the in-patient population with AIT. We expect that we would be able to identify 10-15 cases/year that would qualify for this trial and given the potential acceptance to enrollment we expect that it would take 12-18 months for the trial completion.

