## Subject Information

Target accrual is 5 patients. To achieve this number of subjects, we will access medical records for about 100 patients.

Subject population: Adults ( $\geq 18$  years of age) with AIT who undergo treatment at Mayo Clinic, Rochester and those referred to thyroid clinic for evaluation.

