#### **Data Analysis Plan:**

Sample size has not been calculated as analysis will only include descriptive statistics. Results for continuous variables will be expressed as median and interquartile range, and for categorical variables as proportions.

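### Categorical outcomes in five patients are planned as proportions without intervals, which cannot support the word *safely* in the hypothesis

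*Combined protocol and SAP*

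**What the plan says.** The Hypothesis and the Aims section carry the same proposition: partial ablation will lower thyroid hormones to normal, do so safely, and resolve the thyrotoxicosis. On its link to the study, the Aims section says: "This will address the hypothesis that ablation of a portion of thyroid parenchyma with RFA technique will safely decrease thyroid hormone levels". The sentence before it gives a plainer aim, to study hormone changes after the procedure.

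Study Design makes safety a secondary objective with a one-month window: "The safety of the RFA procedure will be assessed as well (secondary objective) in the first month after the procedure". It also fixes the size and mentions a comparator: "We plan to enroll 5 patients to undergo the procedure and use a historical control group for comparison of clinical and biochemical outcomes". Subject Information repeats the number: "Target accrual is 5 patients".

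The Data Analysis Plan has two sentences. The first is "Sample size has not been calculated as analysis will only include descriptive statistics". The second is "Results for continuous variables will be expressed as median and interquartile range, and for categorical variables as proportions". No confidence interval, acceptable complication rate or safety criterion is given.

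The Rationale explains the scale: "this would be the first study on this therapy, hence our pilot study approach".

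**The concern.** Complications, and normalisation of hormone levels, are naturally categorical outcomes. Under the plan each would be summarised as a proportion of five patients, with nothing to show how imprecise it is. The best possible results, 0% with a complication and 100% normalised, look decisive but say little about the underlying rates.

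At stake is how the result is read. The Rationale describes this as the first study of the therapy in this disease, so its figures may be cited. A reader who sees a hypothesis containing *safely*, followed by a reported 0%, could take the hypothesis as supported when the data would still allow complications to be common.

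**Working it through.** The documents state no power, error rate or derived sample size, so there is no figure of theirs to reproduce. The check asks how much information a proportion from five patients carries.

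**Inputs**
- Patients treated: n = 5 (Study Design; Subject Information).
- Categorical summary: proportions, no interval (Data Analysis Plan).
- Confidence level: none stated. I assume 95%, two-sided, exact binomial (Clopper-Pearson).
- Planned ablation volume: as calculated in case 1, raised by 25% in case 2 and by 50% in case 3, with the approach for the remaining cases decided afterwards (Procedure).

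**No complications, 0/5**
- Two-sided 95% upper limit: 1 − 0.025^(1/5) = 1 − 0.478 = 0.522, or 52%.
- Other conventions: the one-sided 95% exact limit is 1 − 0.05^(1/5) = 0.451, or 45%. The Wilson upper limit is 43%. The range across the three is 43% to 52%.

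**Chance of seeing no event, (1 − p)^5**
- True rate 10%: 0.9^5 = 0.590, or 59%.
- True rate 20%: 0.8^5 = 0.328, or 33%.
- True rate 30%: 0.7^5 = 0.168, or 17%.

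**All normalised, 5/5**
- Two-sided 95% lower limit: 0.025^(1/5) = 0.478, so the interval is 48% to 100%.

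**Intermediate results (exact two-sided 95%)**
- 1/5: 0.5% to 71.6%
- 3/5: 14.7% to 94.7%
- 4/5: 28.4% to 99.5%

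**Limit of the calculation.** The binomial interval assumes one common event probability. The planned volume differs across the first three cases and may change again, so a pooled x/5 does not estimate the rate for any one fixed approach. If the last two patients shared one approach, 0/2 would have a two-sided upper limit of 1 − 0.025^(1/2) = 0.842, or 84%. The pooled interval is a rough guide to precision.

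**The case against.** The strongest reply is that the document already says what kind of study this is. It calls itself a pilot, says that no sample size was calculated, and limits itself to descriptive statistics. The form's Data Analysis section does not require power analyses or endpoints for pilots. The proposition is labelled a hypothesis, and the study is said to address it, not prove it. Hormone levels, the main biochemical outcome, are continuous and get a median and interquartile range. Safety also does not rest on a proportion: the Procedure section sets out peri-procedural monitoring, an early examination and calcium check, follow-up at 1, 2 and 4 weeks, and presentation of data from the first three cases to a monitoring committee. Nothing says that denominators will be dropped or that 0/5 will be declared proof of safety.

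Most of this stands, and it rules out three stronger readings that a reader might infer:
- *That the trial is wrongly sized.* It claims no power, so there is no sample-size error.
- *That it makes a confirmatory claim, or conceals its limits.* The hypothesis is labelled as one, the stated aim is to study hormone changes, and the small, descriptive design is disclosed.
- *That 5/5 would fail to exclude the 50% normalisation figure quoted in the Rationale for toxic nodules and goiters.* That holds two-sided (lower limit 48%). The one-sided 95% lower limit is 0.05^(1/5) = 0.549, or 55%, which excludes 50%. The documents fix no convention, so the point should not lean on this comparison.

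What remains is narrower. Disclosing a small pilot does not attach precision to the reported figures, and an exact interval is itself a descriptive statistic. The planned historical control does not fill the gap: the Data Analysis Plan gives no method for that comparison, and it would not narrow the complication interval in the five treated patients.

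**Conclusion.** The point holds as a minor reporting and wording matter. The hypothesis includes *safely*, while the plan summarises categorical outcomes in five patients without any measure of precision. With no events, complication rates up to about 52% remain compatible with the data (two-sided 95%), and a complication with a true rate of 20% has a one-in-three chance of never appearing. A bare 0% or 100% therefore cannot carry that word.

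The exact figure depends on the assumed 95% level and two-sided convention, and on treating the five patients as having one common rate. The conclusion that precision is very low does not depend on the choice among these conventions, since the upper limit for 0/5 stays at 43% or more. The varying planned volume makes interpretation weaker still.

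**What to change.** In the Data Analysis Plan, state that each categorical outcome will be reported as x/5 with its exact (Clopper-Pearson) two-sided 95% confidence interval, including when x is 0 or 5. Add a case-level listing of outcomes, adverse effects and ablated volume, and note that the pooled interval is only a rough guide because the planned volume differs by case.

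In the Hypothesis and Aims, present safety as a preliminary description. Add a sentence such as: *Five patients cannot establish safety; if no complication is seen, only true rates above about 52% are excluded (two-sided 95%).* Use the same convention throughout.

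The cost is slightly more reporting and a less favourable stated claim. No extra patients are needed, and treatment and follow-up do not change.

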**Background:**

**Background on Condition, Disease, or Other Primary Study Focus**

Amiodarone induced thyrotoxicosis (AIT) is an entity developing in about 2-8 % of patients treated with amiodarone. It is considered to have a dual pathophysiology with increased thyroid hormone production in AIT type 1, and leakage of preformed thyroid hormone in a thyroiditis fashion in AIT type 2. The two types are in reality combined in many patients and combination therapy is required in such patients, which delays the therapeutic response. Furthermore even if combination therapy is used in some cases the response to therapy is suboptimal and the patients have complications related to hyperthyroidism and side-effects from the medications used. We have shown an increase in frequency of hospitalizations, CHF, weight loss and arrhythmia in this group. Some patients require thyroidectomy for adequate control of their thyrotoxicosis , a procedure not without risks in this population with cardiac comorbidities.

**Rationale:**

RFA has been used for the management of thyroid nodules for more than a decade . We have employed it here at Mayo Clinic for the past 4 years with good results . While mainly used for non-toxic thyroid nodules there is encouraging data describing the response to RFA in the case of toxic thyroid adenomas. In total in the literature there are 47 cases of toxic nodules or toxic goiters that were treated with RFA (8-10) and in 50% of these cases the thyroid function normalized and in none of them did thyrotoxicosis worsened as a result of therapy. RFA has the capacity to lead to destruction of thyroid parenchyma and also to denaturation of stored thyroid hormone. Thus it seems to provide the perfect approach to target both mechanisms of AIT in an expeditious manner which is essential in these usually very sick individuals with coexistent cardiac co-morbidities. So far there is no reported data on the efficacy of RFA in AIT and this would be the first study on this therapy, hence our pilot study approach.

[figure not shown]
## Study Design and Procedure

### STUDY DESIGN

This will be an open-label clinical trial that will target AIT patients that fail to respond to medical therapy. We will treat them with RFA therapy and then assess the clinical and biochemical response (primary objective) in the coming 4 weeks and continue to monitor the clinical response for a minimum of 3 months or until the resolution of the AIT episode, whichever occurs later. We expect that an individual will be thus in the trial for a total of 4-6 months. The safety of the RFA procedure will be assessed as well (secondary objective) in the first month after the procedure. We plan to enroll 5 patients to undergo the procedure and use a historical control group for comparison of clinical and biochemical outcomes. The study will take place at Mayo Clinic in Rochester, MN and will recruit both from our out-patient as well as the in-patient population with AIT. We expect that we would be able to identify 10-15 cases/year that would qualify for this trial and given the potential acceptance to enrollment we expect that it would take 12-18 months for the trial completion.

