In the first 48 hours post-procedure we will assess thyroid levels (TT3 and FT4) twice (once between 2 and 8 hours and again between 24 and 48 hours) and calcium level once between 24 and 48 hours. They will also have a brief clinical exam between 24-48h to assess procedure safety. In order to understand the bioactivity and the impact of thyroid hormone released during the procedure resting energy expenditure (REE) by indirect calorimetry will be assessed prior to RFA procedure and again 24 - 72h post RFA procedure; in addition, T3 and T4 research investigation will also be performed for that purpose; for this, separate blood draw for research will be done 48 hr prior to procedure and at E1 and E2 time points (see algorithm above) as well as measuring total T4 to have a better understanding if the measured hormone could be active hormone or a denatured chemical structure. The patients will then be monitored clinically at 2 and 4 weeks and biochemically at 1, 2 and 4 weeks, following thyroid levels and clinical signs and symptoms of thyrotoxicosis along with monitoring the procedure local area for signs and symptoms of adverse effects of the intervention (e.g. pain, swelling, hoarseness, hypocalcemia, skin injury). A final research evaluation will be performed at the time of the clinical follow-up between 3 and 6 months including thyroid values and a research thyroid ultrasound to assess parenchymal changes.

(Please refer to the overview of the study).

*The volume of thyroid parenchyma to be ablated is based on our assumption about linear correlation between serum thyroid hormone levels and total parenchymal volume. We will test this hypothesis and use the first 3 cases to decide if an adjustment to this approach is needed. We will present this data to Data Safety Monitoring Committee and propose modification to the protocol if necessary.*

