## Concomitant Interventions

### Allowed Interventions

*Medical therapy with steroids, antithyroid drugs or both will be ongoing peri-procedure with an increase in the ongoing anti-thyroid regimen the day of RFA and the day after the procedure after which pre-procedure doses will be resumed until thyroid levels are collected at the end of week 1 post-procedure. On a precautionary measure in the event of excess release of active T3 / T4 due to RFA, patients will be administered Lugols iodine solution (5 drops x 3 per day) starting after the procedure and continuing for the first 3 days post-RFA. Beta-blockers will be employed/increased starting 1 day before procedure and then adjusted in a manner analog with anti-thyroid regimen. These adjustments will be made in collaboration with cardiology, according to the cardiovascular status of the patient. If some of these changes are not clinically acceptable then bile-acid sequestrants will be used for their anti-thyroid effect, starting 2 days before procedure and continuing for 3 days after the procedure. If despite these interventions thyrotoxicosis will deteriorate post RFA both plasmapheresis and thyroidectomy will be discussed with the patient and pursued based on the clinical situation.*

*Of note – amiodarone can be continued during the study, at the discretion of the cardiologist consultant.*

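### The safety objective closes at one month although patients are followed to a final evaluation at 3 to 6 months, so later or persisting harms have no planned place in the safety result

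*Combined protocol and SAP*

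**What the plan says.** The hypothesis (Research Question and Aims) includes safety in its claim about RFA. STUDY DESIGN makes safety the secondary objective and limits it in time: "The safety of the RFA procedure will be assessed as well (secondary objective) in the first month after the procedure". The same section says the team will "continue to monitor the clinical response for a minimum of 3 months or until the resolution of the AIT episode, whichever occurs later", and adds: "We expect that an individual will be thus in the trial for a total of 4-6 months".

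PROCEDURE lists the assessments. In the first month these are TT3 and FT4 twice within 48 hours, calcium once, a brief safety examination at 24 to 48 hours, resting energy expenditure at 24 to 72 hours, thyroid levels at 1, 2 and 4 weeks, and clinical review at 2 and 4 weeks. The clinical review covers thyrotoxicosis as well as "monitoring the procedure local area for signs and symptoms of adverse effects of the intervention". The named adverse effects, given twice and as examples only, are pain, swelling, hoarseness, low calcium and skin injury. After week 4 one research visit is described: "A final research evaluation will be performed at the time of the clinical follow-up between 3 and 6 months including thyroid values", with an ultrasound. No adverse-event assessment is named for it.

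Background says of AIT patients: "We have shown an increase in frequency of hospitalizations, CHF, weight loss and arrhythmia in this group". Allowed Interventions foresees worsening: "If despite these interventions thyrotoxicosis will deteriorate post RFA both plasmapheresis and thyroidectomy will be discussed". The Data Analysis Plan promises medians, interquartile ranges and proportions. It names no safety variable and no criterion for calling the procedure safe.

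**The concern.** The one-month limit is a stated rule, not a missing detail. If it is followed as written, a harm that arises or persists after month 1 may be seen at a scheduled visit and still be left out of the result that supports the word safely. It might be reported as part of clinical response, or not at all, and the plan does not say which.

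There is a second gap inside the window. Hormone levels, calcium, energy expenditure and signs of thyrotoxicosis are collected, but apart from low calcium, which is on the example list, nothing says they count as safety outcomes. The serious clinical events that the plan itself mentions (hospitalization, heart failure, arrhythmia, plasmapheresis, thyroidectomy) are not named as safety outcomes in any period.

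The plan describes itself as the first study of RFA in AIT. With 5 patients, its main safety product is a complete account of harms, and each patient is a fifth of the evidence.

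**Working it through.** **1. Figures to reproduce.** There are none. The plan states no safety threshold, event rate, alpha or power, and the Data Analysis Plan says that no sample size was calculated.

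**2. Where each kind of event would fall, reading the sections together.**

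| Event | Observed under the plan? | In the safety objective as written? |
|---|---|---|
| Skin burn, pain or swelling at the procedure | Yes: observation after the procedure, 24 to 48 h examination, weeks 2 and 4 | Yes |
| Early hormone release | Yes: TT3/FT4 twice within 48 h, week 1, energy expenditure | Inside the window, but not designated a safety outcome |
| Hoarseness that starts early and does not resolve | Onset yes; no assessment named after week 4 | Onset yes, persistence no |
| Hospital admission, heart failure or arrhythmia in month 1 | Probably, through clinical review | Not named |
| The same events after month 1 | Possibly, through clinical follow-up | No |
| Plasmapheresis or thyroidectomy for deterioration | Yes, as clinical care | Not named; excluded if after month 1 |
| Low thyroid hormone levels at 3 to 6 months | Yes, in the final thyroid values | No |

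**3. Why low hormone levels are a fair question on the plan's own terms.** PROCEDURE assumes that FT4 is linear in thyroid volume. Its example gives (2.4 − 1.6)/2.4 = 33% of the gland. The calculated volume is raised by 25% in case 2 and by 50% in case 3. For the same example, case 3 would give 33.3% × 1.5 = 50%, unless the safety limits on the ablation zone reduce it. Low levels once the AIT episode resolves are therefore foreseeable, and resolution may come after month 1. This is an inference from the plan's assumption, not a documented rate.

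**4. Effect of one uncounted event with n = 5 (exact Clopper-Pearson, two-sided 95%).**

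- Event counted: 1/5 = 20%. Lower limit 1 − 0.975^(1/5) = 0.005. The upper limit solves (1 − p)^5 + 5p(1 − p)^4 = 0.025, giving p = 0.716. The interval is 0.5% to 72%.
- Event not counted: 0/5 = 0%. Upper limit 1 − 0.025^(1/5) = 0.522. The interval is 0% to 52%.

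**5. What cannot be computed.** The chance that such an event occurs after month 1 needs a late event rate and its distribution over time. The documents give neither.

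**The case against.** The strongest reply is that the window suits its stated object, which is the safety of the procedure. Burns, injury to nearby structures and hormone release occur early. The precautions against hormone release in Allowed Interventions are concentrated around the procedure and its first 3 days, with hormone levels checked at week 1. The AIT events in Background belong to the disease and its drug treatment. Relapse is a failure of response and is already followed as such. The protocol template adds that pilot studies need not specify endpoints.

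Much of this stands, and it rules out several stronger readings that a reader might infer:

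- *That safety is watched only locally.* The documents do not support this. Substantial systemic monitoring is planned in month 1, the adverse-effect list is illustrative, and low calcium is not a local effect.
- *That the harms the plan fears are systemic.* PROCEDURE gives most of its precautions to skin burns and surrounding structures.
- *That most of the harm is missed because one month is only a third to a sixth of a 3 to 6 month follow-up.* That fraction measures time, not risk, and procedural risk may well be front-loaded.
- *That a safety conclusion would be reversed.* The analysis is descriptive, there is no threshold to cross, and the two intervals in the working overlap almost entirely.

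The study overview figure is not shown, so an adverse-event schedule there cannot be excluded. It would not remove the one-month limit that STUDY DESIGN states in words.

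The reply does not explain why an event seen at a planned visit should be left out of the harm summary. Attribution to the disease or to RFA can be discussed once the event is in the table.

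**Conclusion.** The concern holds in a limited form. The safety objective ends at one month while follow-up continues for at least 3, no adverse-event assessment is named after week 4, and the serious systemic events that the plan mentions are not named as safety outcomes. The affected events are those that arise late or persist; acute harms are inside the window.

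The only size that can be stated is conditional: if one patient has such an event and it is not counted, the result reads 0/5 (upper limit 52%) instead of 1/5 (0.5% to 72%). No probability is attached to that, because none can be drawn from the documents. Even 0/5 would not establish safety. This is a worthwhile, inexpensive improvement to the completeness of harm reporting. It is not evidence that the trial would reach a wrong conclusion.

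**What to change.** In STUDY DESIGN, change the safety objective so that safety is assessed from the procedure to the final evaluation at 3 to 6 months, with month 1 tabulated separately. The early procedural result then remains visible.

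In PROCEDURE, add adverse-event recording to the final evaluation, including whether earlier effects such as hoarseness have resolved.

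In the Data Analysis Plan, list the safety outcomes. Beside the local effects and calcium, count hospitalization, heart failure, arrhythmia, worsening thyrotoxicosis including any plasmapheresis or thyroidectomy, and low thyroid hormone levels on the values already drawn. Report each as a number out of 5, with its time from the procedure, and say that 5 patients cannot establish safety.

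The cost is the wording and the recording of adverse events at visits already scheduled; no new visit or test is needed. The safety result may look less favourable, and some late events will reflect the underlying disease rather than RFA, so the report should describe each event and its likely cause.
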